## Study Summary

[figure not shown]
Title	Reducing Arrhythmia in Dialysis by Adjusting the Rx Electrolytes/Ultrafiltration
Short Title	RADAR
Protocol Number	
Phase	Pilot
Methodology	
Randomized, Crossover, Blinded, Multi-arm
 
Interventions:
 
Implanted Loop Recorder
 
Potassium/Bicarbonate Trial (Study A)
 
Ultrafiltration Trial (Study B)

Study Duration	24 months
Study Center(s)	
Duke University Medical Center (DUMC)
 
New York University Langone Health (NYU)-coordinating site receiving funding from the NIH with dialysis unit located at Lower Manhattan Dialysis Center ([name]).

Objectives	
 
• To obtain pilot data on adherence, safety and barriers to implementation of proposed interventions.
 
• To obtain pilot data on recruitment feasibility and subject retention.
 
• To obtain pilot data to estimate the potential effect sizes of proposed interventions.
 

Number of Participants	
40 (20 in each of two interventions)
 
(60 participants enrolled with 40 expected to reach randomization. Because patients have the option of enrolling in both study A and B it is possible that the total number of devices required will be less than 40.)

Diagnosis and Main Inclusion Criteria	Dialysis-dependent end-stage renal disease
Study Product/Intervention, Route, Regimen	
Study A: Potassium/Bicarbonate Four-Arm Crossover
 
Potassium (K) Removal Maximization strategy, 1 month (lower dialysate K)
 
Potassium (K) Gradient-Minimization Strategy, 1 month (higher dialysate K)
 
Acidosis Avoidance, 1 month (higher dialysate bicarbonate)
 
Alkalosis Avoidance, 1 month (lower dialysate bicarbonate)
 
Study B: Dialysis Ultrafiltration Rate (UFR) Two-Arm Crossover
 
UFR <math>\leq</math>10 ml/kg/hr, 1 month
 
UFR as needed, 1 month

Ancillary Products:	
LINQ™ (Medtronic) Implantable Cardiac Loop Recorder (Carelink System)
 
i-STAT (Abbott)- Study A only

Duration of administration	LINQ™: 3-6 months Study A: 4 months Study B: 2 months

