Comparing the impact of alternative dialysis protocols on fatal and non-fatal arrhythmia has been hampered by the sample sizes needed to demonstrate an effect on SCA and practical limitations to monitoring arrhythmia for more than a few days. Thus, data linking dialytic parameters to CV death primarily comes from retrospective analyses of large data-sets which provide proof of concept but do not establish causality. Interventional data is limited and comes from short-term studies measuring changes on surrogate measures such as electrocardiogram morphology during a single dialysis session rather than on arrhythmia incidence. Understanding of the most basic aspect of dialysis care is thus inadequate, and whether simple, achievable changes to the dialysis prescription could improve outcomes remains unknown. Recent advances, however, make long-term cardiac monitoring feasible. The investigators propose studies testing whether altering dialysis potassium (K), bicarbonate (HCO3), or UF prescription lowers the incidence of arrhythmia in HD patients. The proposed pilot studies will leverage this technology to perform first-ever randomized trials to test the effects of differential dialysis prescriptions on the occurrence of arrhythmia over more than a few days, thereby advancing understanding of fundamental, but overlooked aspects of dialysis and the study of cost-effective, implementable interventions that improve the health and well-being of a critically underserved, high- risk population. Lastly, they will provide the necessary and sufficient information for the design of definitive trials.

Significance of Sudden Cardiac Arrest (SCA) and pre-SCA arrhythmias in HD patients—SCA risk increases dramatically as eGFR declines and peaks in ESRD where it is the most frequent cause of mortality accounting for 28% of deaths. This association is independent of coronary disease severity and traditional CV risk factors, and associations between SCA and dialysis timing (**Figure 1**) provide strong evidence that dialysis-specific factors are key triggers of SCA. With 1 in 20 HD patients dying annually from SCA, identifying reversible and treatable dialytic SCA triggers is a key strategy for reducing CV mortality.

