## II. Specific Aims

Overview of Trial Design—The overall goal for these trials is to provide the data necessary for the design of definitive clinical trials. Specifically, we aim to test recruitment feasibility, the feasibility of POC electrolyte measurement and POC-directed management of the dialysis prescription, and to provide preliminary estimates of effect size with manipulation of UF rate, dialysate K, and dialysate HCO3. We will perform two related, randomized cross-over trials; Study A- dialysate interventions trial, consisting of 2 dialysate potassium interventions and 2 dialysate bicarbonate interventions (4 total cross-over interventions); and Study B-ultrafiltration rate intervention trial, consisting of 2 separate ultrafiltration rate strategies.

The central hypothesis underlying Study A and Study B is that the risk of clinically significant arrhythmias in HD patients can be reduced by altering components of the dialysis prescription.

**Aim 1—To test the feasibility and safety of POC-guided dialysate prescription adjustment and the feasibility of limiting UF rate in HD patients.** The current studies will pilot our educational strategies and the dialysate potassium, dialysate bicarbonate and UF intervention strategies to test their feasibility in a multi-center setting. They will test the hypothesis that  $\geq 80\%$  adherence with proposed interventions is feasible, and that the safety need for unscheduled dialysis or severe abnormalities in potassium and bicarbonate will be minimal.

**Aim 2—To assess recruitment feasibility and retention rate for trials combining ILR insertion to monitor arrhythmia and interventions using POC-guided dialysis prescription or UF rate manipulation.** Screen failures and retention rates will be captured and analyzed. Whether recruitment rates  $\geq 1$  patient per month and retention rate  $> 90\%$  are achievable in each study will be tested.

**Aim 3—To refine effect estimates of the change in monthly CSA duration during Study A (dialysate potassium intervention to maximize vs. minimize intradialytic potassium removal) and Study B (aggressive vs. conservative ultrafiltration rate).** Refining estimates of change in CSA with each pair of interventions will provide key information necessary for design of definitive trials. Whether CSA decreases with minimization of potassium removal, alkalosis limitation and UF rate minimization will be tested.

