### ***Early Withdrawal of Participants***

#### **When and How to Withdraw Participants**

Early withdrawals will be discouraged and participants who are not willing to continue the intervention will be encouraged to remain in the study and continue study evaluations. However, participants may be withdrawn from the study under the following circumstances that have the potential to compromise patient autonomy or safety:

- a. Pregnancy
- b. Withdrawal of consent
- c. Allergy to or documented intolerance to ancillary study medications for implant procedure (e.g. lidocaine, versed, xylocaine, or other medications used for local anesthetic or conscious sedation)
- d. Non-compliance with dialysis schedule compromising ability to follow serum potassium on a monthly basis
- e. Organ transplantation
- f. Change to a different dialysis modality
- g. Prolonged hospitalization
- h. Transfer to non-participating dialysis unit
- i. Incarceration

[figure not shown]

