## **V. Description of Study Procedures**

Two related, randomized cross-over trials will be performed; Study A-a dialysate interventions trial, consisting of 2 dialysate potassium interventions and 2 dialysate bicarbonate interventions (4 total cross-over interventions); and Study B- an ultrafiltration rate intervention trial, consisting of 2 separate ultrafiltration rate strategies. A total of 20 patients will be enrolled in each trial. An overview of the study design is illustrated in **Figure 5 below**.

**ILR Intervention**— Consent and ILR placement at the local site will be followed by a one-month baseline observation period. ILR placement will be followed by wound check visits at 1 week and 1-month post implant. Outpatient insertion of ILR by study cardiologists will occur within 4 weeks of enrollment. Reveal LINQ™ (Medtronic) implantable monitors will be utilized.

**Arrhythmia Detection**—Detection of clinically significant arrhythmias (CSA) will be achieved using implantable loop monitors (ILR) inserted at the start of each trial. ILR tracings will be batch analyzed by study cardiologists blinded to randomized treatment. Tracings from ILR-detected events meeting automated, validated detection criteria for bradycardia, asystole, AF, sustained or non-sustained ventricular tachycardia (VT) will be manually reviewed at least once every two weeks. Clinically significant arrhythmias will be defined on the basis of arrhythmias likely to lead to sudden cardiac arrest or serious morbidity and mortality and will include atrial fibrillation (AF), asystole lasting  $\geq 3$  seconds, bradycardia  $\leq 40$  beats per minute lasting  $\geq 6$  seconds, sustained VT  $\geq 130$  beats per minute lasting  $\geq 30$  seconds, and any sudden cardiac arrest. Positively adjudicated CSA will be entered into a study database and coded according to arrhythmia type, date and duration.

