**Safety Endpoints**—The primary safety endpoint will include the incidence of all serious adverse events and intervention-specific complications: a) Potassium Intervention—severe K abnormalities ( $K \geq 6.5$  or  $\leq 3.0$  mEq/L), or unscheduled HD or hospitalization for hyper/hypokalemia in the absence of a missed treatment; b) Bicarbonate Intervention—severe  $HCO_3$  abnormalities ( $HCO_3 < 20$  or  $> 32$  mEq/L) or unscheduled HD or hospitalization for acid base abnormalities in the absence of a missed treatment; c) Ultrafiltration Intervention—Unscheduled HD or hospitalization for volume overload. Secondary safety endpoints include the occurrence of CSAs requiring further management, all-cause mortality, cardiovascular mortality, and hospitalization.

**Recruitment Feasibility (Aim 2)**—Recruitment feasibility will be analyzed by testing whether an overall recruitment rate of 1 patient/month is achieved in each trial (1-sample test). This is a critical metric, as a large-scale trial cannot be feasibly completed in a practical number of centers if between 0.5-1 patient/month cannot be enrolled. This rate represents a minimum criterion for feasibility.

The percent of screened patients enrolled will be calculated as a secondary feasibility measure to assess the size of the necessary screening pool. Reasons for non-enrollment (vis-a-vis inclusion and exclusion criteria and patient and physician preferences) will be assessed to determine the potential for protocol modification to improve recruitment. Subject retention will be calculated as the percentage of enrolled patients completing the trial. Retention rates of 90% will be considered the benchmark for feasibility.

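### The retention benchmark is above 90% in Aim 2 but 90% in Section VI, so 18 of 20 completers fails one and meets the other; the denominator is also unsettled

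*Combined protocol and SAP*

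**What the plan says.** Two sections of the protocol set the retention criterion.

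- Section II (Specific Aims), Aim 2, uses a strict inequality: "retention rate $> 90\%$ are achievable in each study will be tested".
- Section VI (Biostatistical Analysis), under Recruitment Feasibility (Aim 2), gives no inequality sign: "Retention rates of 90% will be considered the benchmark for feasibility". The same paragraph defines the measure: "Subject retention will be calculated as the percentage of enrolled patients completing the trial".

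Two sections describe the number enrolled.

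- Section V (Description of Study Procedures): "A total of 20 patients will be enrolled in each trial".
- Study Summary: "60 participants enrolled with 40 expected to reach randomization", with 20 in each of the two interventions.

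The definition makes no exception for death. The early-withdrawal list in Section IV includes organ transplantation, change of modality and "Transfer to non-participating dialysis unit", so these can also produce non-completers. Section VI plans a confidence interval for adherence but mentions none for retention.

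**The concern.** Retention is listed among the feasibility outcomes in the Study Summary, and Section VI gives it a numerical benchmark. With 20 per trial it moves in steps of five percentage points, and one of those steps falls exactly on 90%. The difference between above 90% and 90% is therefore one whole participant, and 18 completers gives opposite answers in the two sections. That result is likely enough to need settling before data arrive; otherwise the reading could be chosen after the count is known.

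The denominator raises a second question. The definition divides by enrolled patients, and the documents use that word for two different groups. On one of them, the planned loss before randomization already puts the benchmark out of reach.

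**Working it through.** The benchmark is a chosen threshold. The plan gives no pass probability or interval for it, so there is no stated figure to reproduce.

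**1. Threshold as a count.** 18/20 = 90.0% and 19/20 = 95.0%. Strictly above 90% needs 19 or more; at least 90% needs 18 or more.

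**2. Pass probability at a given loss.** With independent losses and retention q, the number retained is Binomial(20, q).

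At q = 0.90:
- P(20) = 0.9^20 = 0.122
- P(19) = 20 × 0.1 × 0.9^19 = 0.270
- P(18) = 190 × 0.1² × 0.9^18 = 0.285
- Strict rule: 0.122 + 0.270 = 0.39. At-least rule: 0.39 + 0.285 = 0.68.

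**3. An illustrative loss from the documents.** The Background says "With 1 in 20 HD patients dying annually from SCA" and puts SCA at 28% of deaths. Together these imply 0.05/0.28 = 17.9% all-cause mortality per year. That rate is derived, not stated. Loss over w weeks is taken as 1 − exp(−0.179 × w/52), with deaths as the only loss.

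| Setting | Loss | Strict (19 or more) | At least 90% (18 or more) |
|---|---|---|---|
| Study A, 23 weeks from ILR | 7.6% | 54% | 81% |
| Study A, 19 weeks from randomization (weeks 5–23) | 6.3% | 64% | 87% |
| Study A, 27 weeks from consent | 8.9% | 46% | 74% |
| Study A, 23 weeks, mortality halved (assumption) | 3.9% | 82% | 96% |
| Study A, 23 weeks, plus 5% other loss (assumption) | 12.2% | 28% | 55% |
| Study B, 12 weeks from ILR | 4.0% | 81% | 96% |

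In the first row, exactly 18 completers has probability 0.809 − 0.545 = 0.26. Reading 17.9% as an annual risk instead of a rate gives 8.3% loss over 23 weeks, with pass chances of 50% and 77%.

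**4. Loss at which passing has probability one half.** This is 8.3% under the strict rule and 13.1% under the at-least rule.

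**5. Denominator.** On the Study Summary's meaning of enrolled, at most 40/60 = 66.7% are expected even to reach randomization. That is below 90% under either inequality.

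**6. Precision.** The exact (Clopper-Pearson) 95% interval for 18/20 is 68% to 99%.

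**The case against.** The strongest reply is that this is a one-symbol discrepancy in a pilot. Section VI calls the analyses exploratory and conservatively interpreted. The description as a minimum criterion is reserved for the recruitment rate, and nothing makes proceeding to a definitive trial depend on retention. That is correct: a reader might infer a go/no-go rule, but the documents do not set one. A numerical benchmark still needs one value, and the conflict stands.

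A reader might also infer that background mortality alone makes the Study A benchmark close to a coin flip. The documents do not support that as a general statement.
- It holds only under Aim 2's strict inequality. Under Section VI, mortality alone leaves 74–81% over 23 to 27 weeks on the rate form.
- The 17.9% combines two figures from different source reports, and the documents state no all-cause rate.
- The eligibility criteria exclude expected survival under 6 months and transplant, home or peritoneal dialysis, or transfer to a non-study facility anticipated within 6 months, so actual loss may be lower.
- It does not carry over to Study B.

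A third inference is that deaths, transplants and transfers should be removed from the score because they say nothing about trial burden. That does not follow. A definitive trial must absorb all-cause attrition, which is what the pilot is meant to inform. The risk section allows that protocol-driven prescription could in theory raise arrhythmia risk, and Section VI counts hospitalization for volume overload as an intervention-specific complication. Dropping such events could hide harm. Nor are all listed events automatic failures: Section IV says participants may be withdrawn, and Section V lets people return after long absences and complete.

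**Conclusion.** The two sections conflict, and the conflict decides the result at 18 of 20. The choice of rule moves the pass probability from 39% to 68% when true retention is 90%, and from about 54% to 81% for Study A at a 7.6% loss. For Study B the shift is about 81% to 96%. The 90% case rests only on n = 20 and independent losses. The other figures also rest on the derived mortality, before any effect of the exclusion criteria, and on no other loss; the documents give no transplant, transfer or dropout rates.

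The denominator is a separate inconsistency. With 20 per trial the benchmark is attainable; with the Study Summary's 60 it is not, under either inequality. Counting all-cause completion is a defensible choice and is not part of the defect.

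**What to change.** - State one inequality and its count in both Aim 2 and Section VI, for example at least 18 of 20, with the rule to apply if the final number is not 20.
- Name one denominator, for example randomized participants, and use it in the Study Summary, Section V and Section VI. Since the ILR is placed before randomization, report loss between enrollment and randomization separately, so that attrition around insertion stays visible.
- Report retention in each study with an exact 95% confidence interval.
- Keep all-cause completion as the benchmark measure. Beside it, describe non-completion by reason: death, transplant, transfer, modality change, consent withdrawal, loss to follow-up and other listed reasons. This should not replace the benchmark.

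The cost is wording plus one recorded reason per non-completer. The plan specifies reasons for non-enrollment but not for non-completion, so that item should be added explicitly. Visits, treatments and sample size do not change.

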#### **Data Collection and Follow-up for Withdrawn Participants**

In the case of withdrawal, every attempt will be made to obtain consent to continue to follow patients for the occurrence of mortality, hospitalizations, and other safety signals via telephone or in-person contact with participants, relatives, and dialysis unit staff and records until scheduled end of follow-up.

Participants will be deemed as lost to follow-up after  $\geq 3$  attempts have been made to contact the patient via their preferred means of contact (telephone or email),  $\geq 1$  attempt has been made to contact the patient via their secondary means of contact, and  $\geq 1$  attempt to contact next of kin is unanswered.

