## **VI. Biostatistical Analysis**

Given an overarching aim to assess definitive trial feasibility, analyses will be considered exploratory and conservatively interpreted but no adjustment will be made for multiple comparisons.

**Trial Endpoints and Overview of Specific Aims:** The long-term goals are to conduct well-powered trials testing the effect of POC testing-guided management of dialysate potassium and bicarbonate or limitation of maximum UF rate on clinically significant arrhythmia (CSA) and hard cardiovascular events. The specific goals of Studies A/B in accordance with the R34 funding mechanism isto provide the key feasibility and effect-size data necessary to plan definitive, subsequent multi-center trials. Towards this end, data on:

- Aim 1: Adherence with Proposed Interventions
- Aim 2: Recruitment Feasibility
- Aim 3: Effect Estimates

**Adherence with Proposed Interventions (Aim 1)**— In routine practice, the dialysis prescription is adjusted by the physician only once per month in response to monthly laboratory results. Utilizing POC testing and daily adjustment of the dialysate prescription deviates from this standard considerably. Similarly, while a post-dialysis target weight is prescribed by dialysis providers, in routine practice, patients and nurses have daily discretion regarding UF rate. In short, protocolizing the interventions represent a significant change from standard of care that will require active engagement of both patients and HD-unit staff. Estimating the extent of protocol deviation and the safety of proposed interventions in this environment is critical to large-scale implementation of the proposed trials as biologic efficacy is immaterial if interventions cannot be scaled-up.

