**Effect Estimates (Aim 3)**—Estimating the mean and standard deviation (SD) of the change in duration of clinically significant arrhythmia (CSA) per month is critical for power and sample size calculation and planning definitive studies. The total monthly duration of CSA (in minutes) will be utilized as the primary efficacy endpoint in comparing each pair of interventions (K removal maximization vs. minimization, acidosis vs. alkalosis avoidance, aggressive vs. conservative UF). In the event of incomplete follow-up, CSA duration will be indexed to follow-up time. CSA will be defined on the basis of arrhythmias likely to lead to SCA or serious morbidity and mortality and will include AF, asystole  $\geq 3$  seconds, bradycardia  $\leq 40$  beats per minute lasting  $\geq 6$  seconds, and sustained VT  $\geq 130$  beats per minute lasting  $\geq 30$  seconds. CSA's will be adjudicated by study electrophysiologists.. Currently, no data exists on the expected impact of the interventions on CSA duration, but given a mean duration of CSA in MiD of  $356 \pm 1765$  minutes, a sample size of 20 subjects provides 80% power for detection of change in CSA duration of 140 minutes/month given within-subject correlation of 0.9, 370 minutes for within-subject correlation of 0.7, and 470 minutes if within-subject correlation is 0.5.

**Statistics and Analysis**—A balanced, uniform crossover design will be used with randomization stratified by site in blocks of 4.

**Adherence** will be estimated as % (95% CI) of sessions without protocol deviation. Comparison of adherence percentage pre- vs. post-interim analysis of adherence will be made using linear regression with time period as an independent variable. Exploratory analyses will assess association of adherence with site, dialysis shift (1st-3rd), and day (Monday/Wednesday/Friday or Tuesday/Thursday/Saturday).

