**Safety** will be assessed by calculating the incidence rate (complications per unit follow-up time) for serious adverse events and intervention-specific complications. Comparisons of incidence rate between interventions will utilize Poisson regression adjusted for randomization scheme and site. Exploratory analyses will assess age, sex, race, mean intra-dialytic weight gain, potassium concentration and HCO3 concentration in month prior to randomization on the incidence of adverse events. Given the pilot nature of the trials and major goal of informing feasibility estimates for definitive trials, P<0.05 will be considered significant in all safety analyses. No adjustments will be made for multiple comparisons given the pilot nature of the studies.

**Efficacy** estimates for Aim 3 will utilize the mean duration of CSA as the primary outcome. In the event of incomplete follow-up, this will be indexed to duration of follow-up time (e.g. minutes per day). Change in CSA duration between interventions will be analyzed using mixed effects linear regression with terms for treatment, research site, period, sequence, and random effects for subjects. Primary outcomes for the dialysate trial will compare CSA during potassium maximization vs. minimization, and acidosis vs. alkalosis avoidance. For the UF trial, aggressive vs. conservative UF will be compared. Physiologically, the washout period of 1-week in the dialysate trial and 1 weekend in the UF trial is sufficient to avoid the possibility of carryover effects. Potential for sequence effects is minimized by a design with uniform sequences (all treatments appear once within each sequence). Potential for carryover and randomization sequence effects will be analyzed by including terms for sequence and their interaction with treatment in the models.

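### The power statement counts all 20 randomised patients per trial as complete within-patient comparisons and makes no allowance for loss after randomisation; in Study A this costs about 2 to 5 points of power

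*Combined protocol and SAP*

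**What the plan says.** The Study Summary (Number of Participants) plans 20 patients in each of two trials and explains the route to that number: "60 participants enrolled with 40 expected to reach randomization". The margin between 60 and 40 therefore covers loss before randomisation only.

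Section VI, Effect Estimates (Aim 3), states that "a sample size of 20 subjects provides 80% power for detection of change in CSA duration of 140 minutes/month", continuing "given within-subject correlation of 0.9, 370 minutes for within-subject correlation of 0.7, and 470 minutes if within-subject correlation is 0.5". The SD behind these figures is 1765 minutes, taken from the earlier monitoring study. The calculation is within-patient, since the detectable change depends on a within-subject correlation.

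Under Recruitment Feasibility (Aim 2) the same section says: "Retention rates of 90% will be considered the benchmark for feasibility". It counts enrolled patients who complete the trial. Specific Aims, Aim 2, sets the target as more than 90%.

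Section IV (When and How to Withdraw Participants) lists transplantation, change of modality, transfer to a non-participating unit and prolonged hospitalisation as grounds for withdrawal. For withdrawn patients, "every attempt will be made to obtain consent to continue to follow patients for the occurrence of mortality, hospitalizations, and other safety signals". Arrhythmia duration is not named there.

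**The concern.** A within-patient comparison needs data under both strategies. In Study A the four strategies are given in random order, in month-long periods separated by washout weeks. A patient who leaves for one of the listed reasons cannot receive the remaining assigned dialysate strategies, so one or both pairs (potassium, bicarbonate) may stay incomplete. The power statement makes no provision for this, and the sample size of 20 is met only at 100% retention.

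At stake is whether the published sensitivity of the pilot matches the data it expects to have. The omission is also independent of the SD used. Recomputing the detectable changes on a consistent SD, but still with 20 pairs, would give values slightly too small for Study A.

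**Working it through.** **Inputs.** 20 randomised per trial (Study Summary). SD 1765 and correlations 0.9, 0.7 and 0.5 (Section VI, Aim 3). Retention 90% (Section VI, Aim 2) or above 90% (Specific Aims). Alpha is stated only for safety, "P<0.05 will be considered significant in all safety analyses"; two-sided 0.05 is assumed here for efficacy. On multiplicity the plan says "no adjustment will be made for multiple comparisons", so none is applied.

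**Step 1: the plan's own figure.** The SD of the within-patient difference is 1765 × √(2(1 − r)).

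| r | SD of difference | Printed change | Power at printed change, 20 pairs | Same, 18 pairs |
|---|---|---|---|---|
| 0.9 | 789 | 140 | 11.4% | 10.6% |
| 0.7 | 1367 | 370 | 20.9% | 19.1% |
| 0.5 | 1765 | 470 | 20.4% | 18.6% |

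Power is from the noncentral t with n − 1 degrees of freedom. The printed 80% is not reproduced. Other alpha levels, one-sided tests and other variance formulas were tried, and none gives all three changes. By the normal approximation, the SDs that would reproduce them are about 500, 762 and 750, so no single SD fits. The effect of attrition must therefore be measured relative to a change that really has 80% power with 20 pairs.

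**Step 2: number of pairs.** 20 × 0.90 = 18. Because 18/20 is exactly 90%, a target of more than 90% needs at least 19 of 20 (95%).

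**Step 3: power.** With 20 pairs, 80% power requires a change of 0.660 SD of the difference. Holding that change fixed:

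| Pairs | Power | Detectable change at 80% power, relative to 20 pairs |
|---|---|---|
| 20 | 80.0% | 1.000 |
| 19 | 77.7% | 1.029 |
| 18 | 75.2% | 1.061 |
| 17 | 72.5% | 1.096 |

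Averaging over a binomial number of completers (20 patients, 90% each) gives 75.0%. One-sided 0.05 gives 75.9% at 18 pairs. These ratios do not depend on the SD or the correlation.

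**Step 4: detectable changes on the plan's SD.** Multiply the SD of the difference by 0.660 (20 pairs), or by 0.660 × 1.061 = 0.701 (18 pairs):

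| r | 20 pairs (min/month) | 18 pairs (min/month) |
|---|---|---|
| 0.9 | 521 | 553 |
| 0.7 | 903 | 958 |
| 0.5 | 1166 | 1237 |

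**Step 5: partial data in Study A.** If all orders are equally likely, a patient who has completed 0, 1, 2 or 3 periods holds both periods of a given pair with chance 0, 0, 1/6 or 1/2. If those four exit points are equally likely (assumption), the average is (0 + 0 + 1/6 + 1/2)/4 = 1/6, so two dropouts return 2 × 1/6 ≈ 0.3 of a pair. A mixed model with treatment and period terms under the same dropout assumption recovers a little more, about half a pair. That gives roughly 18.5 effective pairs and 76% power.

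**Step 6: Study B.** Strategies alternate weekly for eight weeks, so a patient who leaves after the first two treatment weeks has been observed under both. Only earlier departures lose the comparison altogether.

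**The case against.** Several points on the other side are sound. The 90% figure is a feasibility criterion to be evaluated, not a dropout rate assumed for sizing. Its denominator is also unclear. If enrolled means the 60 in the Study Summary, completion could not exceed 40/60, about 67%; Section V, however, uses enrolled for the 20 in each trial. The target of more than 90% points to 19 pairs, where the loss is only about 2 points.

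Non-completion is not the same as losing the pair. Patients unwilling to continue the intervention are encouraged to stay for evaluation, loop-recorder data upload automatically, and Study A periods can be extended for missed treatments. Arrhythmia duration is indexed to follow-up time, and the mixed model imposes no complete-pair rule. Step 5 shows that this recovers part of the loss, but not most of it: indexing rescues a shortened period, not one that never started.

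The analyses are declared exploratory, and Aim 3 is about estimating a mean and SD, so no decision turns on 80% against 75%. Nor need the omission pass into the definitive trial, because Aim 2 measures retention directly. All of this limits the weight of the point. None of it supplies the missing allowance.

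**Conclusion.** The point stands as a minor correction. The power statement uses the number randomised as the number analysed and makes no allowance for later loss. If the benchmark is read against the 20 randomised, Study A keeps about 18 to 19 complete pairs. A change with true 80% power at 20 pairs then has about 75% to 78%, or a detectable change 3% to 6% larger. Partial data reduce the loss slightly, and Study B loses little. The result rests on an assumed two-sided alpha of 0.05 and on the reading of the retention denominator.

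A reader might infer that Study A has about 75% power at 140, 370 or 470 minutes, or that those values need only be scaled up by 6%. The documents support neither. With SD 1765 the power at those changes is about 11% to 21% with 20 pairs, and attrition to 18 removes only 1 to 2 points. The inconsistency between the printed changes and the SD is the larger defect in the same sentence, and this point is secondary to it.

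**What to change.** Make one revision to the power sentence in Section VI, Effect Estimates (Aim 3), together with the correction of its SD:

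- Compute the detectable changes on a consistent, stated SD of the within-patient difference, for the expected number of evaluable pairs: about 18 of 20 in Study A and nearer 20 in Study B. If SD 1765 is kept, the Study A values at 18 pairs are about 553, 958 and 1237 min/month for correlations of 0.9, 0.7 and 0.5.
- State alpha and sidedness for the efficacy comparison.
- State whether retention is counted on patients enrolled or randomised, and whether the benchmark is 90% or more than 90%.
- Add a line that Study B patients with at least one week on each strategy contribute to the comparison.

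The cost is a rewritten sentence or two and a less favourable stated sensitivity. No extra patients, procedures or enrolment are needed.
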